2. LIST OF ABBREVIATIONS

Include a list of all abbreviations used in the TSAP

Term	Definition / description
ADR	Adverse Drug Reaction
AE	Adverse event
ALT	Alanine aminotransferase
AST	Aspartate aminotransferase
BSA	Body surface area
FEV_1	Forced Expiratory Volume in 1 second
FVC	Forced Vital Capacity
НОТ	Home Oxygen Therapy
IIPs	Idiopathic Interstitial Pneumonias
IPF	Idiopathic Pulmonary Fibrosis
MedDRA	Medical Dictionary for Regulatory Activities
MMF	Mycophenolate Mofetil
MMRM	Mixed Effects Model for Repeated Measures
NIS	Non-interventional Study
OCS	Oral corticosteroid
PD	Protocol deviation
PT	Preferred term
Q1	Lower quartile
Q3	Upper quartile
RMP	Risk Management Plan
SAE	Serious Adverse Event
SD	Standard deviation
SMQ	Standardised MedDRA query
SOC	System organ class
TBILI	Total bilirubin
ToC	Table of contents
TSAP	Trial statistical analysis plan

3. INTRODUCTION

The purpose of this document is to provide a more technical and detailed elaboration of the principal features of the analysis described in the protocol, and to include detailed procedures for executing the statistical analysis of the post-marketing surveillance (PMS) data.

This TSAP assumes familiarity with the Non-interventional Study (NIS) Protocol, including Protocol Amendments. In particular, the TSAP is based on the planned analysis specification as written in NIS Protocol Section 9.7 "DATA ANALYSIS". Therefore, TSAP readers may consult the NIS Protocol for more background information on the study, e.g., on study objectives, study design and population, treatments, definition of measurements and variables, planning of sample size."

SAS® Version 9.4 or later will be used for all analyses.

4. CHANGES IN THE PLANNED ANALYSIS OF THE STUDY

Covariance matrix was changed from "compound symmetry" specified in NIS protocol to "unstructured" in MMRM (Mixed Effects Model for Repeated Measures) analysis.

Added the following events to priority survey items because they were added in Japanese RMP.

5. ENDPOINT(S)

5.1 PRIMARY ENDPOINT(S)

There is no primary endpoint for effectiveness, the primary objective of the PMS study is the evaluation of safety (see the NIS Protocol Section 10.3.2).

5.2 SECONDARY ENDPOINT(S)

5.2.1 Key secondary endpoint(s)

This section is not applicable as no key secondary endpoint has been specified in the NIS protocol.

5.2.2 Secondary endpoint(s)

The secondary endpoints will be used as stated in the NIS Protocol Section 10.3.2.

6. GENERAL ANALYSIS DEFINITIONS

6.1 TREATMENT(S)

For basic study information on treatments, please refer to NIS Protocol Section 5. The technical specification for treatment set-up is described in the analysis data set (ADS) plan. For safety analyses, data up to 28 days after last treatment intake will be considered as ontreatment.

6.2 IMPORTANT PROTOCOL DEVIATIONS

Provide a table specifying the definition of all important PDs with columns for PD category / code, PD description, additional comment/example and a column to describe which PDs will be used to exclude patients from the different patient analysis sets. The final decision about which patients will be excluded from analysis sets will be taken during the course of the study and at report planning meetings before database lock at the latest.

Table 6.2: 1 Important protocol deviations

	egory /	Description	Requirements	Method	Excluded from
Cod	ie	Enduce as suitaris and made			
A		Entrance criteria not met	1		
	A1	Patient of non-approved	Non-IPF patient	Manual	Effectiveness
		Indication			
В		Trial medication			
	B1	No treatment with Ofev®		Automat	Safety/Effectiven
		Capsules		ed	ess
C		Missing data			
	C1	No patient visit after	No visit made after the entry	Automat	Safety/Effectiven
l		registration		ed	ess
	C2	No safety observation was	No AE occurrence	Manual	Safety/Effectiven
l		documented after registration	information and details		ess
	C3	No FVC and FVC% value at	None of value about FVC	Automat	Effectiveness (for
		baseline and/or at post	and FVC % predicted for	ed	FVC and %FVC
		treatment	effectiveness analysis, at		analysis only)
			baseline and/or at post		
			treatment		
	C4	No data reliability	No signature by contracted	Manual	Safety/Effectiven
			investigator in book1		ess
D		Invalid registration			
	D1	Required registration	After the approval condition	Manual	Safety/Effectiven
		procedure was not followed	has been removed. See NIS		ess
			protocol section 10.2.2.2.		
	D2	Patient started Ofev®	After the approval condition	Automat	Safety/Effectiven
		Capsules treatment out of	has been removed See NIS	ed	ess
		registration period	protocol section 10.2.2.2.		
E		Contract			
	E1	No valid site contract		Manual	All(registration)

6.3 SUBJECT SETS ANALYSED

The safety set will be the basis of all demographic, baseline and safety analyses. Effectiveness analysis will be done on the basis of the effectiveness set.

• Safety set:

This patient set includes all patients who didn't have any IPDs leading to exclusion from this analysis set as defined in Table 6.2: 1.

• Effectiveness set:

This patient set includes all patients with Ofev® Capsules in the safety set who were suffering from the approved indication. Further IPDs leading to exclusion from this analysis set are defined in Table 6.2: 1.

In FVC and %FVC analysis, patients with FVC and %FVC value at baseline and post treatment in effectiveness set are used.

Subject sets analysed Table 6.3: 1

	Subject set	
Class of endpoint	Safety set	Effectiveness set
Primary endpoints	X	
(other) Secondary and further endpoints		X
Safety endpoints	X	
Treatment exposure	X	X
Demographic/baseline endpoints	X	

6.5 POOLING OF CENTRES

This section is not applicable because centre is not included in the statistical model.

6.6 HANDLING OF MISSING DATA AND OUTLIERS

Safety:

Missing or incomplete AE dates are imputed according to BI standards (('Handling of Missing and Incomplete AE Dates' (1))).

Missing or partial date information other than AE and treatment dates will be replaced according to the following rules.

Effectiveness:

Missing effectiveness data will not be imputed.

Missing or partial date information will be replaced according to the following rules.

YEAR	MONTH	DAY	YMD	DT
"Unknown" (tick-box)		UNKNOWN		
уууу	Null or "Unknown"	Null	уууу	yyyy/01/01
уууу	mm	Null or "Unknown"	yyyymm	yyyy/mm/01

If the date of data which is collected after treatment of Ofev[®] Capsules in the CRF is before start of Ofev[®] Capsules, they will be set to missing.

Demographics:

Missing or partial date information in birth date will be replaced according to effectiveness

Treatment exposure:

Date of last Ofev® Capsules intake:

To calculate duration of Ofev® Capsules treatment at an interim analysis, the date is imputed with the following date according to the book number.

Book1: the first treatment date $+365.25/12 \times 3$

Book2: the first treatment date +365

Book3: the first treatment date $+365+(365.25/12\times6)$

Book4: the first treatment date +730 days.

Missing or partial date information will be replaced according to the following rules.

YEAR	MONTH	DAY	YMD	DT
уууу	mm	Null or "Unknown"	yyyymm	yyyy/mm/the last day of the month
уууу	mm	The beginning of the month	yyyymm	yyyy/mm/10
уууу	mm	The middle of the month	yyyymm	yyyy/mm/20
уууу	mm	The end of the month	yyyymm	yyyy/mm/ the last day of the month

Note that in general when tabulating AEs, and/or demographic and baseline characteristics variables reported as unknown will be treated as such; otherwise treated as missing data.

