6.7 BASELINE, TIME WINDOWS AND CALCULATED VISITS

With regard to effectiveness and safety endpoints, the term "baseline" refers to the last observed measurement before administration of Ofev[®] Capsules. The first date of the administration of Ofev[®] Capsules is included in "baseline".

Effectiveness analyses will be performed based on calculated visits as shown in Table 6.7: 1. If two or more data points of a patient fall into the same interval, the closest value to the planned day will be selected. If there are two observations which have the same difference in days to the planned day or if there are two observations on the same day, the first value will be used.

Baseline, time windows and calculated visits Table 6.7: 1

		Time window (act	ual days on treatment)
Week label	Planned days	Start	End
Baseline	1		measurement before of Ofev® Capsules
Week 4	28	2	59
Week 13	91	60	136
Week 26	182	137	227
Week 39	273	228	318
Week 52	364	319	409
Week 65	455	410	500
Week 78	546	501	591
Week 91	637	592	682
Week 104	728	683	End of study

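### Partial effectiveness dates are moved to the start of the month or year with no floor at first dose, so some on-treatment FVC values drop out of their visit

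*SAP*

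**What the plan says.** Section 6.6, under Effectiveness, introduces its date table with "Missing or partial date information will be replaced according to the following rules". The table always takes the earliest possible date: 1 January when only the year is known, the 1st of the month when year and month are known. The same section says that missing effectiveness values are not imputed.

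The sentence after the table begins "If the date of data which is collected after treatment of Ofev" and, for dates before the start of the drug, ends "Capsules, they will be set to missing". Neither the table nor this sentence sets a lower bound at first dose, exempts imputed dates, or fixes the order of the two steps.

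The table has other uses. Birth dates follow it ("Missing or partial date information in birth date will be replaced according to effectiveness"), and the Safety part has a similar lead-in ("Missing or partial date information other than AE and treatment dates will be replaced according to the following rules").

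Section 6.7 assigns visits by days on treatment. It counts the first-dose day as baseline (the sentence opening "The first date of the administration of"), and Week 4 covers days 2 to 59. When several values share a window, "the closest value to the planned day will be selected". Section 6.3 adds that for FVC and %FVC "patients with FVC and %FVC value at baseline and post treatment in effectiveness set are used".

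**The concern.** The two rules work against each other. The first moves a partial date as far back as it can go; the second treats a date before first dose as grounds for discarding a post-treatment value. Nothing recorded about such a value says it preceded treatment. The pre-treatment date comes only from the imputation.

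Reading the rules differently does not save the value:

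- **Impute, then check (the natural order):** the value is set to missing and is not replaced.
- **Check recorded dates only:** the value survives the check but still carries a date before day 1, which fits no post-baseline window.
- **Only the date is set to missing:** an undated value cannot be placed in a window.

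If treatment began on the 1st of a month, the value lands on day 1, which counts as baseline. It could displace the true baseline only if baseline is derived by date alone.

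The MMRM in section 7.5.2 uses every post-baseline visit and reports LS means at each, so Week 4 is an estimated time point. A patient whose only post-treatment FVC is lost this way also leaves the FVC analysis under section 6.3.

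**Working it through.** The SAP gives no figure on this point, so there is none to reproduce. The check applies the section 6.6 rules to calendar dates and reads the result against Table 6.7: 1.

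**Inputs.** From the SAP: the imputed dates (section 6.6) and the windows, with the first-dose day as day 1 (section 6.7). Assumed: first dose equally likely on each of 365 days of a non-leap year; true FVC date either on the planned day or evenly spread over the window; imputation before the check. All percentages are conditional on a partial date.

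**Example.** First dose 10 June, FVC on 28 June (day 19, Week 4), day unknown. The imputed date is 1 June, nine days before first dose, and the value is set to missing.

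**Unknown day: values in the start month.** A month of length L has L(L−1)/2 pairs of first dose and later measurement.

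- All pairs: 7×465 + 4×435 + 378 = 5373.
- First dose on the 1st (imputed date is day 1): sum of (L−1) = 365 − 12 = 353.
- Imputed date before start: 5373 − 353 = 5020.

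Every such measurement falls on days 2 to 31, so only Week 4 is exposed.

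- *Even spread over days 2-59:* 365 × 58 = 21,170 pairs. Before start 5020/21,170 = 23.7%; on day 1 353/21,170 = 1.7%; together 25.4%.
- *Measured on day 28:* first dose and measurement share a month for 7×4 + 4×3 + 1 = 41 start dates, 12 of them on the 1st. Before start 29/365 = 7.9%; on day 1 12/365 = 3.3%; together 11.2%.

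A leap-year set of start dates gives 8.2% + 3.3% (day 28) and 23.8% + 1.7% (even spread).

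**Unknown day: later visits.** The shift is at most 30 days. Planned day to window start is 91 − 60 = 31 days at Week 13 and 45 days from Week 26 on, so on-schedule values neither vanish nor move. Under an even spread some move one window back. The mean shift is 5373/365 = 14.7 days, so the share is 14.7/77 = 19.1% at Week 13 and 14.7/91 = 16.2% for the 91-day windows (about 16% at Week 104, whose window is open-ended).

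**Unknown month: on-schedule values.** For true day d, the imputed study day takes each value from d − 364 to d once over the 365 start dates. The share before start is (365 − d)/365, and zero once d exceeds 365. The share kept in its own window is (d − window start + 1)/365.

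| Visit (day) | Before start | In own window |
|---|---|---|
| Week 4 (28) | 337/365 = 92.3% | 27/365 = 7.4% |
| Week 13 (91) | 274/365 = 75.1% | 32/365 = 8.8% |
| Week 26 (182) | 183/365 = 50.1% | 46/365 = 12.6% |
| Week 39 (273) | 92/365 = 25.2% | 12.6% |
| Week 52 (364) | 1/365 = 0.3% | 12.6% |
| Weeks 65 to 104 | 0% | 12.6% |

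At day 728 the remaining 87.4% go to Weeks 91, 78 and 65 (24.9% each) and Week 52 (12.6%).

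**Scale.** If 1% / 5% / 10% of Week 4 dates lack the day (assumed), the share of all Week 4 values affected is 11.2% times these, or 0.11% / 0.56% / 1.12%, on schedule. Under an even spread it is 25.4% times these, or 0.25% / 1.27% / 2.54%.

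**The case against.** The strongest reply is that the trigger is undocumented and the effect small. The SAP does not say that FVC dates are ever partial. The table is generic and also serves birth dates, so a year-only row is no evidence that year-only FVC dates occur. The year-only percentages are the most striking and the least supported. There is no primary effectiveness endpoint, the named time point for FVC is Week 104, and the unknown-day rule leaves on-schedule Week 104 values alone. All of this stands, and it limits the weight of the point.

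A lost value is also not always an empty visit. Section 6.7 keeps one value per window, so a patient with another dated Week 4 value still has that visit. The Week 4 percentages are therefore upper bounds for empty visits. That stands too.

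The pre-start check may have been meant as an error check on recorded dates. This does not remove the problem, because visits are assigned by date and an imputed date before day 1 has no window. The displacement of baseline is speculative and carries no weight here.

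Finally, moving dates forward to a floor swaps one convention for another. That is true, but the floored date is compatible with what was recorded, and for start-month values it always falls in the true window.

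**Conclusion.** The concern holds as a minor flaw in the rules. As written, section 6.6 removes genuine on-treatment FVC values from their visit, and no reading of its two sentences prevents this. With unknown day, outright loss is confined to Week 4: 7.9% to 23.7% of such values, plus 3.3% to 1.7% placed on day 1. With unknown month it reaches on-schedule values up to Week 52, and most later values move to an earlier visit, including at Week 104.

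These figures rest on evenly distributed start dates and on imputation preceding the check. The share of partial dates is unknown. The effect is nil if all FVC dates are complete, and about 0.1% to 2.5% of Week 4 values if 1% to 10% lack the day. Nothing shows that a planned result would change materially.

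**What to change.** In section 6.6, for effectiveness data that the CRF records as post-treatment:

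1. **Floor.** Where the partial date is compatible with a date after first administration, use the later of the table date and the day after first administration. If the recorded month or year ends on the day of first administration, use that day; the value then enters no post-baseline visit. Never treat a post-treatment record as baseline because of an imputed date.
2. **Deletion.** Apply the pre-start rule only to complete recorded dates, or to a recorded month or year that ends before first administration.
3. **Year-only dates.** Do not use an imputed 1 January, or its floored date, to choose a visit window. Leave the value out of the by-visit analysis unless a nominal visit is recorded. A floor alone would, for example, put a year-only Week 26 value from the start year into Week 4.

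Keep the present table for baseline values, birth dates and any other dates that share it.

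**Effect.** None of the 5373 start-month cases is lost, and all fall on day 2, inside Week 4.

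**Cost.** Two or three clauses and a small change to the derivation, with these drawbacks:

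- Floored values sit on average 9.5 days, and at most 29, before the true day.
- Day 2 is 26 days from planned day 28, so a floored value yields to any dated value on days 3-53.
- A day-unknown value truly taken on the first-dose day but recorded as post-treatment would count as Week 4 for 353 of 365 start dates. For the other 12, the last days of months, it stays on day 1.
- A patient whose only post-treatment FVC is dated by year alone, with no nominal visit, still contributes nothing by visit.
- Day-unknown values that slip one window back from Week 13 on are not corrected.

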7.8.1 Adverse events

Unless otherwise specified, the analyses of adverse events (AEs) will be descriptive in nature. All analyses of AEs will be based on the number of patients with AEs and NOT on the number of AEs.

Furthermore, for analysis of AE attributes such as duration, severity, etc. multiple AE occurrence data on the CRF, will be collapsed into AE episodes provided that all of the following applies:

[figure not shown]
- The same MedDRA lowest level term was reported for the occurrences
- The occurrences were time-overlapping or time-adjacent (time-adjacency of 2 occurrences is given if the second occurrence started on the same day or on the day after the end of the first occurrence)
- Treatment did not change between the onset of the occurrences OR treatment changed between the onset of the occurrences, but no deterioration was observed for the later occurrence

For further details on summarization of AE data, please refer to BI standards ('Analysis and Presentation of Adverse Event Data from Clinical Trials' (2))

AE analyses will be carried out after integrating AE data from CRF and AE data from Local PV safety database (Perceive).

In addition, events coded as "no adverse event", etc. will not be included in the AE analyses. The list of codes will be provided by Drug Safety.

The frequency of patients with the following items will be summarized by primary SOC and PT.

An ADR is defined as an AE for which either the investigator or the sponsor (or both) assess the causal relationship to Ofev® Capsules either as "Yes "or "Unknown". A serious AE is defined as an AE for which either the investigator or the sponsor (or both) assess the seriousness as "Serious".

The SOCs will be sorted according to the standard sort order specified by European Medicines Agency, PTs will be sorted by frequency (within SOC).

will also be reported by intensity. The frequency of patients having hepatic dysfunction at baseline with will be summarized. Patients with summarized by IIPs severity grade
To compare the risk of experiencing at least one ADR, in different patient subgroups, frequency tabulation stratified by different patient subgroups will be provided with odds ratios and exact 95% confidence intervals whenever specified (see Section 6.4). Logistic regression models will be used and odds ratios together with 95% confidence intervals will be provided.

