Frequency tabulation of stratified by different patient subgroups (the following items) will be provided with odds ratios and exact 95% confidence intervals whenever specified. Logistic regression will be used for odds ratio.
Frequency tabulation of stratified by different patient subgroups (the following item) will be provided with odds ratios and exact 95% confidence intervals whenever specified. Logistic regression will be used for odds ratio.
Frequency tabulation of stratified by different patient subgroups (the following concomitant medications) will be provided with odds ratios and exact 95% confidence intervals whenever specified. Logistic regression will be used for odds ratio.

In addition, summaries for the time to onset of first episode for the ADRs will be tabulated, by duration (<=31, >31 to 91, >91 to 182, >182 to 273, >273 to 364, >364 to 455, >455 to 546, >546 to 637, >637 to 728, >728 [days]), by primary SOC, and PT.

The time to onset of the first adverse drug reaction categorized into priority survey items and diarrhoea will be tabulated by the time(0 to 14, 15 to 30, 31 to 60, 61 to 90, 91 to 180, 181 to 270, 271 to 360, 361 to 540, 541 to 727, =>728 [days]) and summarised.

Incidence rate of _____, ADRs and ______ will be summarized by person-year method, too. Pearson-year is defined as:

- if the patient has the event: date of onset of the first event date of first administration of Ofev® + 1 day
- if the patient did not have the event: date of last administration of Ofev® date of first administration of Ofev® + 1 day

Kaplan-Meier plots including the number at risk will be prepared for

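### Interim person-year rates are biased upward if the PV database holds events after the last collected book, because event-free patients stop at the book day and patients with such events do not

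*SAP*

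**What the plan says.** Four rules in the SAP bear on an interim person-year rate.

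- **Exposure (Section 6.6, Treatment exposure).** For treatment duration "at an interim analysis, the date is imputed with the following date according to the book number". The offsets depend on the book, for example "Book2: the first treatment date +365" and "Book4: the first treatment date +730 days". Book 1 uses three average months, and Book 3 uses 365 days plus six average months. The rule does not say that it is limited to patients still on treatment.
- **Events (Section 7.8.1).** "AE analyses will be carried out after integrating AE data from CRF and AE data from Local PV safety database". No limit to the period covered by the last collected book is stated.
- **Person-time (Section 7.8.1).** A patient with the event contributes time from first administration to onset, plus one day. The other branch reads "if the patient did not have the event: date of last administration of Ofev", less the first administration date, plus one day.
- **On-treatment window (Section 6.1).** For safety, "data up to 28 days after last treatment intake will be considered as ontreatment". The SAP does not say whether an imputed last intake starts this window.

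**The concern.** Each rule is workable alone, but together they give patients different follow-up according to outcome. Take two patients who are both still on drug and have only Book 1 collected. One has an event at day 200 that reaches the PV database. This patient enters the numerator and contributes about 200 days. The other has no event and contributes about 91 days, although this patient was also at risk to day 200 and beyond. After the book day, patients add time only if they have an event, so the denominator is too small for the numerator.

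Safety is the primary objective (Section 5.1), and ADRs are among the items to be summarised by person-years. An interim rate built this way could be read as a higher risk when it only reflects how many books are outstanding. Rates at successive interims could also shift as books arrive.

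**Working it through.** **Inputs from the SAP.** Book offsets in days: Book 1, 365.25/12 × 3 = 91.31; Book 2, 365; Book 3, 365 + 365.25/12 × 6 = 547.63; Book 4, 730. The person-time formula is that of Section 7.8.1 and the window is 28 days (Section 6.1). The SAP states no rate, so there is no figure to reproduce.

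**Assumptions, not in the SAP.** Constant hazard λ of 0.05 to 2 per person-year; true time on drug T at the interim, lying between the patient's book day D and the next book day; share c of first events between D and T that are in the PV database. The extra day in the formula is ignored.

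**Formula.** With X the time to first event:

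- P1 = 1 − exp(−λD), and P2 = exp(−λD) − exp(−λT)
- counted events = P1 + c·P2
- counted time = E[X; X ≤ D] + c·E[X; D < X ≤ T] + D·(1 − P1 − c·P2)
- ratio = (counted events / counted time) / λ

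For small λ this is close to (D + c(T − D))/D.

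**Worked case.** 1,000 Book 1 patients, λ = 0.5 per year, T = 300 days, c = 1:

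- First events by day 300: 337, of which 118 fall by day 91.
- Time from patients with events: 128.9 person-years.
- Time from the 663 without events, as counted: 663.2 × 91.31/365.25 = 165.8. Their true time is 663.2 × 300/365.25 = 544.7.
- Counted rate: 337/(128.9 + 165.8) = 337/294.7 = 1.14 per year. True rate: 337/673.6 = 0.50.
- With the 28-day window on the imputed date: 151 events over 236 person-years, or 0.64 per year, and 337 − 151 = 186 on-treatment first events are not counted.
- With events and exposure both cut at day 91: 118/235 = 0.50.

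**Range for Book 1.** Ratio of computed to true rate. The first three columns have T = 365 and no cap; the fourth applies the 28-day window to the imputed date with c = 1.

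| λ per year | c = 10% | c = 50% | c = 100% | 28-day window |
|---|---|---|---|---|
| 0.05 | 1.29 | 2.40 | 3.72 | 1.30 |
| 0.2 | 1.25 | 2.14 | 3.10 | 1.29 |
| 0.5 | 1.19 | 1.80 | 2.37 | 1.28 |
| 1 | 1.12 | 1.48 | 1.77 | 1.25 |
| 2 | 1.05 | 1.19 | 1.31 | 1.20 |

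With T = 180 and λ = 0.05, the uncapped ratios are 1.10, 1.48 and 1.95.

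**Later books**, with full capture, no cap and T at the next book day: Book 2 gives 1.47 down to 1.06 and Book 3 gives 1.31 down to 1.02 over the same hazards. With the 28-day window these become 1.07 to 1.02 and 1.05 to 1.01.

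**All patients together.** Suppose 20% or 40% of patients have Book 1 only and are really at day 180 (0.493 years), the rest have one full year correctly counted, and the hazard is small. With full capture the ratio is (0.2 × 0.493 + 0.8)/(0.2 × 0.25 + 0.8) = 1.06, or (0.4 × 0.493 + 0.6)/(0.4 × 0.25 + 0.6) = 1.14. With c = 25%, 0.493 is replaced by 0.25 + 0.25 × 0.243 = 0.311, giving 1.01 or 1.03. These shares are illustrations.

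**After the fix.** Cutting events and exposure at the same date gives 1.00 in every scenario.

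**The case against.** The strongest reply is that the imputation exists only to calculate treatment duration and need not feed the person-year denominator. That is weak: the denominator for event-free patients uses the date of last administration, and the SAP gives no other value for patients still on drug at an interim.

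Other replies have more force.

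- A reader might infer that the PV database is fed continuously and always runs ahead of the books. The SAP says only that the sources are integrated. The bias needs at least some PV events later than the last book, and a data cut may be set in the protocol or the analysis data set plan, which are not at hand.
- The SAP does not say that person-year rates will be produced at an interim. The point applies if they are.
- A reader might say that late events fall outside the counted exposure. They do not: a patient with a late event is counted to onset. The fault lies in the truncated time of the event-free patients.
- A reader might take a two- to fourfold inflation as the expected size. That needs nearly full capture, a long gap, a low hazard and no 28-day limit. Applied to the imputed date, the window holds the Book 1 ratio to about 1.3 at most, but it then discards events in patients who are still on drug.
- The AE analyses are descriptive, so no test or decision rule depends on these rates.

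**Conclusion.** The point holds for interim person-year rates. Under the stated rules, the rate is biased upward whenever the PV database contains first events after the last collected book, and the SAP has no sentence that prevents this. The effect is largest for patients with only Book 1 and for rare events.

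The size cannot be fixed from the SAP, because it depends on the hazard, the time since the last book and the share of later events captured. For Book 1 patients it lies between close to 1.0 and about 3.7, and across all patients it is diluted by those with later books.

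It would go too far to say that every interim result is wrong or that the final analysis is affected: the imputation by book is confined to interim analyses. This is a minor but cheap correction.

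**What to change.** Add to Sections 6.6 and 7.8.1:

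1. In interim person-year rates, each patient's events and exposure are cut at the same date. Where last intake is imputed, only events with onset up to the imputed date count. A patient whose first event is later counts as event-free to that date.
2. PV events after that date are listed separately until the next book arrives.
3. Imputation by book number applies only to patients with no recorded stop date.

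Moving last intake forward to the latest PV report is not a substitute. Event-free patients without a report would still stop at the book day, and follow-up would depend on having an event reported. The 28-day rule in Section 6.1 needs no change for these rates.

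The cost is a few sentences and a small program change. The drawback is that later events appear in listings, not in rates, until the next book is collected.
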